#### **3.2.2. Secondary Outcome Measures**

- Incidence of an ANDV-specific titer of  $\geq 20$  on Day 57 (3 dose regimen), Day 85 (4 dose regimen) and Day 197 (3 and 4 dose regimen) as measured by:
  - Plaque reduction neutralization titers
  - Pseudovirion neutralization titers
- Incidence of seroconversion (defined as a post-vaccination ANDV-specific titer  $\geq 40$  if baseline titer  $<20$  or a minimum four-fold rise compared to baseline if baseline titer  $\geq 20$ ) on Day 57 (3 dose regimen), Day 85 (4 dose regimen) and Day 197 (3 and 4 dose regimen) as measured by:
  - Plaque reduction neutralization titers
  - Pseudovirion neutralization titers

### 3.2.3. Exploratory Outcomes

- Incidence of a  $>3$  standard deviation increase in ANDV-specific, cytokine-secreting CD4+ and CD8+ cells on Day 29 (3 and 4 dose regimen), Day 57 (3 dose regimen), Day 85 (4 dose regimen), Day 169 (3 and 4 dose regimen) and Day 197 (3 and 4 dose regimen) compared to baseline (Day 1) as measured by flow-based intracellular staining (ICS).
- Incidence of a  $>3$  standard deviation increase in ANDV-specific CD4+ and CD8+ cells on Day 29 (3 and 4 dose regimen), Day 57 (3 dose regimen), Day 85 (4 dose regimen), Day 169 (3 and 4 dose regimen) and Day 197 (3 and 4 dose regimen) compared to baseline (Day 1) as measured by a lymphoproliferation assay (LPA). Incidence of an ANDV-specific titer of  $\geq 20$  at additional time points as measured by: Pseudovirion neutralization titers/Plaque reduction neutralization titers

### 3.3. Study Definitions and Derived Variables

The term “vaccination group” refers to dose of study product and number of doses that subjects are randomized to receive. Therefore, there are five vaccination groups: ANDV DNA 2mg 3 doses, ANDV DNA 2mg 4 doses, ANDV DNA 4mg 3 doses, ANDV DNA 4mg 4 doses, and placebo. The placebo group will include all subjects who received placebo from all cohorts. Results will also be displayed for all subjects where indicated.

Seroconversion is defined as a post-vaccination ANDV-specific titer  $\geq 40$  if baseline titer  $< 20$  or a minimum four-fold rise compared to baseline if baseline titer  $\geq 20$ .

Geometric mean fold rise (GMFR) represents the geometric mean fold rise in antibody compared to baseline, calculated as the arithmetic mean of the difference in log antibodies back-transformed to the original scale.

Baseline is considered to be the last measurement taken prior to the first vaccination.

The lower limit of quantitation (LLOQ) for both PRT and PsVNA assay results is 20. Any values less than the LLOQ will be assigned a value of 14.1 by the lab. This imputed value will be used for the purpose of calculating summary statistics such as mean and GMT. All corresponding descriptive statistics that are  $< \text{LLOQ}$  will be reported as “ $< 20$ ” in summary tables.

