### **3.2. Endpoints**

#### **3.2.1. Primary Outcome Measures**

- Occurrence of vaccine-related Serious Adverse Events (SAEs) through approximately 6 months post last vaccination.
- Occurrence of vaccine-related unsolicited Adverse Events (AEs) through 28 days post last vaccination.
- Occurrence of Serious Adverse Events (SAEs) through approximately 6 months post last vaccination.
- Occurrence of unsolicited Adverse Events (AEs) through 28 days post last vaccination.
- Occurrence of solicited local and systemic AEs through 7 days after each study vaccination.
- Occurrence of clinical safety laboratory AEs through 7 days after each study vaccination.

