#### **4.3.6. Blinding**

Except for the sentinel subjects who receive study vaccine open label, this is a double-blind trial. Sentinel subjects are blinded to dose schedule, but not dose level. Vaccine is prepared by an unblinded pharmacist who refers to the Treatment Key provided for the trial by the SDCC to determine the treatment for the subjects. The study products are administered by an unblinded study product administrator. The unblinded vaccine administrator is not involved in study-related assessments and does not have subject contact for data collection following study vaccine administration. Investigators, study personnel performing any study-related assessments following study vaccine administration, and laboratory personnel performing antibody assays are blinded to treatment arm assignment (i.e., placebo vs. study vaccine, and dose regimen).

A designated individual at the VTEU site was provided with a code list for emergency unblinding purposes, which is kept in a secure place. Additionally, in the case of a medical emergency, the PI or ISM may deem it medically necessary to unblind the subject's treatment assignment. If the PI or ISM believes that unblinding would benefit the medical care of the subject and time permits, DMID is consulted prior to unblinding, and concurrence is obtained. After DMID has approved the unblinding, an independent medical doctor or appropriate designee at the site, who is NOT the principal investigator or blinded staff, is to contact the SDCC. If the independent medical doctor or designee cannot make contact with SDCC staff, and/or time does not permit, the unblinding process can occur on-site by contacting the unblinded pharmacist or study staff.

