## 8. IMMUNOGENICITY EVALUATION

This study was not designed to test a specific null hypothesis; rather, the primary objectives include assessing the safety and tolerability of two dosages and two dose regimens of an ANDV DNA vaccine as compared to a placebo administration.

Immunogenicity and cellular assay data summaries and analyses will be presented by vaccination group for the ITT population, and for the PP population in the event of major protocol deviations (as defined in Section 6.3.2) or if any subjects are found to be ineligible at baseline. Summary statistics for continuous data will include mean, standard deviation (SD), median, minimum and maximum. For titer data, geometric mean and 95% CI will be calculated in place of arithmetic mean and standard deviation. Number of subjects, percentage (with denominator defined as the number of subjects with non-missing data), and exact (Clopper-Pearson) 95% confidence intervals will be presented for proportional endpoints.

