## 9.1 Overall Study Design and Plan Description

**Table 1: Study Design**

Cohort	Subjects Enrolled	Randomization/ Treatment Arm*#	Day 1	Day 29	Day 57	Day 169
Cohort 1 2mg ^	12	1a* n=1 Sentinel	ANDV DNA	ANDV DNA	Placebo	ANDV DNA
		1b# N=9 ANDV DNA	ANDV DNA	ANDV DNA	Placebo	ANDV DNA
		1c# n=2 Placebo	Placebo	Placebo	Placebo	Placebo
Cohort 2 2mg ^	12	2a* n=1 Sentinel	ANDV DNA	ANDV DNA	ANDV DNA	ANDV DNA
		2b# N=9 ANDV DNA	ANDV DNA	ANDV DNA	ANDV DNA	ANDV DNA
		2c# n=2 Placebo	Placebo	Placebo	Placebo	Placebo
Cohort 3 4mg +	12	3a* n=1 Sentinel	ANDV DNA	ANDV DNA	Placebo	ANDV DNA
		3b# N=9 ANDV DNA	ANDV DNA	ANDV DNA	Placebo	ANDV DNA
		3c# n=2 Placebo	Placebo	Placebo	Placebo	Placebo
Cohort 4 4mg +	12	4a* n=1 Sentinel	ANDV DNA	ANDV DNA	ANDV DNA	ANDV DNA
		4b# N=9 ANDV DNA	ANDV DNA	ANDV DNA	ANDV DNA	ANDV DNA
		4c# n=2 Placebo	Placebo	Placebo	Placebo	Placebo
TOTAL		48 subjects				

\* All sentinel subjects and study personnel will be unblinded to dose and blinded to treatment schedule.

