## 16.2.7 Adverse Events

### Listing 9: 16.2.7.1: Solicited Events – Systemic Symptoms

[Implementation Note: Indicate severity for quantitative symptoms (e.g., temperature, measurements), by including the grade in parentheses after the number, e.g., 100.7 (Mild). Sort order: Vaccination Group, Subject ID, Dose Number, Post Dose Day, Symptom.]

Vaccination Group	Subject ID	Dose Number	Post Dose Day	Assessment a	Symptom	Severity	Attributed to Alternate Etiology? b	Alternate Etiology
				MA				
				Clinic				

a MA = Data reported by subject on the Memory Aid and reviewed by clinic staff and reported in Solicited Events eCRF.

Clinic = Data collected by clinic staff during physical exam or symptom assessment (treatment administration record, in-clinic assessment, etc.)

b Grade 3 events in all subjects, Grade 2 and 3 events in sentinel subjects.

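### One open-label sentinel sits unmarked in each ten-subject vaccine column; a sentinel flag and randomised-only rows would keep the placebo comparison blinded

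*SAP*

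**What the plan says.** SAP 3.3 defines five vaccination groups. A group "refers to dose of study product and number of doses that subjects are randomized to receive", and "The placebo group will include all subjects who received placebo from all cohorts". SAP 6.3.3 defines the Safety population as all subjects given at least one dose.

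The design table (SAP Table 1, the same as Protocol Table 1) shows one sentinel per cohort (for Cohort 1, "1a* n=1 Sentinel"), nine further vaccine recipients and two placebo recipients. Protocol 5.4.1 and SAP 4.3.3 randomise sentinels 1:1 to dose regimen only. The other 22 subjects in each dose stage are randomised 9:2:9:2 to vaccine or placebo in the two regimens.

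On masking, SAP 4.3.6 states: "Except for the sentinel subjects who receive study vaccine open label, this is a double-blind trial". The Table 1 footnote adds: "All sentinel subjects and study personnel will be unblinded to dose and blinded to treatment schedule".

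SAP 8 describes the primary objectives as "assessing the safety and tolerability of two dosages and two dose regimens of an ANDV DNA vaccine as compared to a placebo administration", and SAP 4.1 also frames the study as a comparison with placebo. The primary outcomes include solicited events and "Occurrence of vaccine-related unsolicited Adverse Events (AEs) through 28 days post last vaccination".

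In Listing 9, the column on attribution to an alternate etiology carries this footnote: "Grade 3 events in all subjects, Grade 2 and 3 events in sentinel subjects". Listings 9–11 identify subjects by vaccination group and ID, with no sentinel column. SAP 6 to 9 contain no analysis with the sentinels set apart.

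**The concern.** The SAP calls the trial double-blind and sets the vaccine columns beside placebo, but one subject in ten on the vaccine side is open label and had no chance of receiving placebo. Most systemic solicited symptoms, and local pain and tenderness, are graded by interference with daily activity (Protocol 9.2.2). Relatedness is a clinician's judgement (Protocol 9.2.1). Both can respond to knowing that vaccine was given, and both feed primary outcomes.

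No hypothesis is tested, so the displayed rates are themselves the result. SAP 2.1 and 6.6 allow group-level results to be published. A reader of those tables could not tell that the columns mix blinded and open-label subjects, and could not remove the open-label part.

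Listing 9 has a separate, practical defect. For a Grade 2 systemic event, a blank in the attribution column could mean that no alternate cause was found (sentinel) or that the question did not apply (non-sentinel). Nothing on the row says which.

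**Working it through.** **1. Are sentinels in the columns?** No sentence says so directly. The group definition has no sentinel category, and the Safety population takes everyone dosed. SAP Table 3 uses N = 10 and N = 20, which equal 9 + 1 and 18 + 2. Its entries follow from 1 − (1 − p)^N: at p = 5%, N = 10 gives 1 − 0.95^10 = 40.1% and N = 20 gives 64.2%. All 18 printed entries reproduce to 0.1 point. The plan's own sample-size figures therefore count the sentinels.

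**2. Share of open-label subjects (from Table 1).**

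| Column | Sentinels / total | Share |
|---|---|---|
| Each regimen group | 1/10 | 10% |
| Each dose level | 2/20 | 10% |
| All vaccine recipients | 4/40 | 10% |
| Placebo arms | 0/8 | 0% |

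A blinded assessor who knows the allocation ratio puts a non-sentinel's chance of being on vaccine at 18/22 = 81.8%. For a sentinel it is 100%.

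**3. Expected shift.** Let b be the blinded rate and o the rate under open-label reporting. The column's expected rate is 0.9b + 0.1o, so the shift is 0.10 × (o − b). The documents give no value for o − b. Assumed differences of 10, 30 and 70 points give shifts of 1, 3 and 7 points. The upward ceiling is 0.10 × (1 − b), which reaches 10 points only when b = 0.

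**4. Shift in one realised column.** A single sentinel's yes or no moves an n = 10 column by 10 points. For example, 3/9 is 33.3% (exact 95% CI 7.5–70.1%). Adding the sentinel makes it 3/10 = 30% (6.7–65.2%) or 4/10 = 40% (12.2–73.8%).

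**5. Cost of separating the sentinels.** For zero events the Clopper-Pearson upper limit is 1 − 0.025^(1/n).

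| n | Upper limit for 0/n |
|---|---|
| 9 / 10 | 33.6% / 30.8% |
| 18 / 20 | 18.5% / 16.8% |
| 8 (pooled placebo) | 36.9% |
| 4 (placebo in one stage) | 1 − 0.025^(1/4) = 60.2% |

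The chance of seeing at least one event at a true rate of 5% is 37.0% with N = 9 (40.1% with 10) and 60.3% with N = 18 (64.2% with 20).

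**6. Where the open-label status does not reach.** Sentinels and staff are masked to schedule, so neither knows whether the Day 57 injection is vaccine or placebo. The post-dose-3 tables are not open label in the same sense. Table 69 is titled as all placebo including Cohorts 1 and 3. If that adds all 20 three-dose vaccinees, two sentinels appear in that placebo display too: 2/(8 + 20) = 7.1%.

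**The case against.** The best defence is that inclusion is deliberate and disclosed. Both documents describe the open-label sentinels several times, and the sample-size table counts them. The trial is descriptive, so no error rate or power is affected, and the safety shells show per-group percentages and intervals with no vaccine–placebo difference. All of that stands. It is why the sentinels should stay in the Safety columns.

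The likely size is also limited. In the related trials described in Protocol 2.1.1, injection-site pain occurred in 28/31 subjects with electroporation. With the gene gun, tenderness followed 79–89% of doses and pain 48–56%. If such rates applied here, the upward ceiling would be 0.10 × (1 − 28/31) = 1.0 point for the first, 1.1–2.1 points for tenderness and 4.4–5.2 for gene-gun pain. Those are other delivery systems, and the gene-gun figures are per dose, so this is only illustrative. One placebo event moves that column by 1/8 = 12.5 points, more than a sentinel can move a vaccine column.

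A reader might infer that sentinels' harms are collected and attributed under different rules. The documents do not support that. Windows, solicited terms, grading scales and the related/not-related definition are the same for everyone (Protocol 9.1 and 9.2; SAP 4.4.1 and 9.3). The Listing 9 difference mirrors the halting rules, which turn on Grade 2 or higher solicited events in sentinels and Grade 3 in the trial at large (Protocol 9.5). On the shells it feeds no summary table and does not enter the vaccine-related primary outcomes.

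A reader might also infer that removing sentinels leaves a clean randomised comparison of 36 against 8. It does not. Randomisation and masking hold within each dose stage (Protocol 5.4.1 and 5.4.2), so the concurrent comparison is 18 against 4, twice. Dose level was randomised for nobody.

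**Conclusion.** The point holds as a cheap improvement. Ten percent of each vaccine group and dose-level column is open label, against none of the placebo arms, and the planned outputs neither mark these subjects nor show results without them. This could affect subjective solicited events and relatedness judgements after doses 1, 2 and 4, and the any-dose summaries built on them.

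The expected shift is 0.10 × (open-label minus blinded rate), bounded by 10 points. Any figure inside that bound rests on an assumed difference in reporting. Upward bias is plausible, but the documents do not establish its direction, so the stronger conclusion that vaccine-side harms will be overstated does not follow. The unreadable blank in Listing 9 does not depend on any bias. The conclusion rests on the planned Table 1 counts and on reading SAP 3.3 with 6.3.3 as pooling the sentinels, which the Table 3 sample sizes support.

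**What to change.** - **SAP 3.3:** say that sentinels are assigned to vaccine and randomised only to schedule, and that they are counted in the vaccination group for their dose and regimen.
- **Safety columns:** leave the sentinels in, with N = 10 and 20, so that the tables still match Table 3.
- **Listings 9–11:** add a sentinel flag.
- **Tables 47, 49–50, 52–55, 57–58, 97–98 and 100–101:** add rows for randomised double-blind subjects only (9 per group, 18 per dose level), and base vaccine-versus-placebo statements on those rows. The tables specific to dose 3 are left out because the Day 57 injection is masked for sentinels too.
- **Placebo:** in the same tables show it pooled (8) and by dose-escalation stage (4 for Cohorts 1/2, 4 for Cohorts 3/4), because randomisation holds only within stage.

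No new data are needed. The cost is SAP wording, extra table rows and slightly wider vaccine-side intervals in the added rows. The stage-specific placebo rows are very imprecise (0/4 has an upper limit of 60.2%), which is a reason to show both placebo versions.

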## 4. INVESTIGATIONAL PLAN

### Overall Study Design and Plan

This is a Phase 1, randomized, placebo controlled, double-blind, dose escalation trial of 48 males and non-pregnant females, 18-49 years old, inclusive, who are in good health and meet all eligibility criteria. This trial is designed to assess the safety, reactogenicity and immunogenicity of an ANDV DNA vaccine for the prevention of Hantavirus Pulmonary Syndrome (HPS). ANDV DNA vaccine or placebo will be administered using the PharmaJet Stratis® Needle-Free Injection System. This study is investigating administration of 2mg and 4mg doses delivered in 3 and 4 dose regimens.

The first 24 participants in Cohorts 1 and 2 include two sentinel subjects since this is a first-in-human Phase 1 study. Sentinel subjects receive 2 mg of study vaccine in an open label manner in a 3 or 4 dose regimen. One sentinel subject is vaccinated, followed for one day for safety and reactogenicity, and when no halting rules are met, the second sentinel subject receives study vaccine in an open-label manner. The two sentinels are followed for safety through Day 8 (laboratory and solicited/unsolicited AEs) and when no pre-defined halting rules are met and no safety concerns identified, enrollment of the 22 remaining subjects in Cohorts 1 and 2 proceeds. While safety data are evaluated for the sentinel subjects, no new subjects are enrolled, but screening continues.

The 22 non-sentinel subjects in Cohorts 1 and 2 are randomized in a 9:2:9:2 ratio (See [Table 1](#) for study design) to receive either placebo or study vaccine (at a dose of 2 mg) in a 3 or 4 dose regimen, in double-blind fashion. The SMC reviews all available safety data through 7 days post second vaccination for all 24 subjects in Cohorts 1 and 2 and provides recommendations to proceed to Cohorts 3 and 4. While safety data are being evaluated by the SMC, no new subjects are enrolled, but screening for Cohorts 3 and 4 and vaccination of the remaining doses in Cohorts 1 and 2 continues.

The 24 participants in Cohorts 3 and 4 follows the same schedule as outlined for Cohorts 1 and 2 above. Sentinel subjects receive 4 mg of study vaccine open label in a 3 or 4 dose regimen and are followed for safety through Day 8. The remaining 22 non-sentinel subjects in Cohorts 3 and 4 are randomized in a 9:2:9:2 ratio (Treatment Arms 3b:3c:4b:4c) to receive placebo or study vaccine at a dose of 4 mg in a 3 or 4 dose regimen, in double-blind fashion.

Doses 2-4 for all vaccination groups are administered per the schedule outlined in [Table 2](#), assuming no halting rules are met. As the vaccine was expected to be well-tolerated based on previously published studies in humans demonstrating the safety of Hantavirus DNA vaccines that use the same plasmid backbone [7], more than one dose was planned to better investigate safety and immunogenicity.

Reactogenicity is measured by the occurrence of solicited injection site symptoms and through 7 days post each vaccination. Unsolicited non-serious AEs are collected from the time of first study vaccination through approximately 28 days after last vaccination. SAEs occurring from the time of study vaccination through approximately 6 months after the last study vaccination are collected. Clinical safety labs are collected on Day 1 and 169, and 7 days after each vaccination; if labs are abnormal, they are repeated at the next scheduled visit (sooner if medically indicated) and followed to normal or stabilization.

Immunogenicity testing includes evaluation of the cellular immune response to ANDV peptide pools and assessment of humoral immune response as measured by ANDV Pseudovirion Neutralization Assay (PsVNA) and by ANDV Plaque Reduction Neutralization Test (PRNT). PBMCs are collected to be used in the cellular assays, flow-based ICS, and LPA for secondary and exploratory immunogenicity endpoints. The duration of this trial for each subject is approximately 12 months.

See [Table 1](#) and [Figure 1](#) for study design.

## 4.1. Discussion of Study Design, Including the Choice of Control Groups

This study is intended to examine the safety and immunogenicity of two doses of ANDV vaccine administered in two dose regimens as compared to placebo. The control group receives a placebo saline solution because there is currently no FDA-licensed vaccine for HPS or ANDV.

## 4.2. Selection of Study Population

### 4.2.1. Study Inclusion Criteria

Prospective subjects must meet all of the following inclusion criteria to be considered eligible for enrollment:

1. Provide written informed consent before initiation of any study procedures.
2. Are able to understand and comply with planned study procedures and be available for all study visits/phone calls.
3. Males or non-pregnant females ages 18-49, inclusive.
4. Are in good health\*

*\*As determined by medical history and physical examination to evaluate acute or currently ongoing chronic medical diagnoses or conditions, defined as those that have been present for at least 90 days which would affect the assessment of the safety of subjects or the immunogenicity of study vaccinations. Chronic medical diagnoses or conditions should be stable for the last 60 days (no hospitalizations, ER or urgent care for condition and no adverse symptoms that need medical intervention such as medication change/supplemental oxygen). This includes no change in chronic prescription medication, dose, or frequency as a result of deterioration of the chronic medical diagnosis or condition in the 60 days prior to enrollment. Any prescription change that is due to change of health care provider, insurance company, etc., or that is done for financial reasons, as long as in the same class of medication, will not be considered a deviation of this inclusion criterion. Any change in prescription medication due to improvement of a disease outcome, as determined by the site principal investigator or appropriate sub-investigator, will not be considered a deviation of this inclusion criterion.*

*Subjects may be on chronic or as needed (prn) medications if, in the opinion of the site principal investigator or appropriate sub-investigator, they pose no additional risk to subject safety or assessment of reactogenicity and immunogenicity and do not indicate a worsening of medical diagnosis or condition. Similarly, medication changes subsequent to enrollment and study vaccination are acceptable provided there was no deterioration in the subject's chronic medical condition that necessitated a medication change, and there is no additional risk to the subject or interference with the evaluation of responses to study vaccination. Note: Topical, nasal, and inhaled medications (apart from steroids as outlined in the Subject Exclusion Criteria), herbals, vitamins, and supplements are permitted.*

5. Oral temperature is less than 100.0 °F (37.8°C).
6. Pulse is 47 to 105 beats per minute (bpm), inclusive.
7. Systolic blood pressure (BP) is 85 to 150mm Hg, inclusive.
8. Diastolic blood pressure (BP) is 55 to 95 mm Hg, inclusive.
9. Have acceptable screening laboratories\*;\*\* within 28 days prior to enrollment.

*\*Refer to Appendix B of the protocol for range of acceptable laboratory values.*

*\*Screening laboratory values that are outside acceptable range but are thought to be due to an acute condition or due to laboratory error may be repeated once. [see Manual of Procedures (MOP)]*

10. Urine protein screen is negative or trace.
11. Drug screen for opiates is negative.
12. HgbA1C <6.3% at screening.
13. HIV – 1/2 antibody negative.
14. HCV antibody negative.
15. HBsAg negative.
16. Women of childbearing potential\*, must be using an effective method of contraception\*\* from 30 days prior to the first study vaccination until 90 days after the last study vaccination.

*\*Women of childbearing potential are defined as those who have not been sterilized via tubal ligation, bilateral oophorectomy, hysterectomy, or successful Essure® placement (permanent, non-surgical, non-hormonal sterilization) with history of documented radiological confirmation test at least 90 days after the procedure (or with use of another birth control method if history of confirmation test not confirmed), AND are still menstruating or < 1 year since the last menses if perimenopausal.*

*\*\*For this study, we define an effective contraceptive method as one that results in a failure rate of less than 1% per year when it is used consistently and correctly. This includes, but is not limited to, non-male sexual relationships, abstinence from sexual intercourse with a male partner, monogamous relationship with a vasectomized partner, male condoms with the use of applied spermicide, intrauterine devices, NuvaRing®, and licensed hormonal methods such as implants, injectables or oral contraceptives (“the pill”).*

17. Women of childbearing potential\* must have a negative serum pregnancy test at screening and a negative urine pregnancy test within 24 hours prior to each study vaccination.

*\*See definition of women of childbearing potential above.*

18. Sexually active male participants whose partner is a woman of childbearing potential\* and has not had a vasectomy\*\* must agree not to father a child until 90 days after the last vaccination\*\*\*.

*\*See definition of women of childbearing potential above.*

*\*\*Performed > 1 year prior to screening*

*\*\*\*Must agree to use a barrier method of birth control e.g., either condom with spermicidal foam/gel/film/cream or partner reports usage of occlusive cap (diaphragm or cervical/vault caps) with spermicidal foam/gel/film/cream/suppository.*

19. Women agree to not donate eggs (ova, oocytes) and male subject agrees not to donate sperm from the start of screening onwards until at least 90 days after the last vaccination.
20. Agree not to participate in another clinical trial during the study period.
21. Agree not to donate blood to a blood bank for 3 months after receiving the last study vaccine.

